4.2.1.2 Exploratory analyses and subgroup analyses of the primary efficacy variable

Subgroup analyses on the primary efficacy variable, and its components, will be performed to evaluate variation of treatment effect. The subgroups in [Table 1](#) will be examined in Cox regression models with a factor for treatment. Kaplan-Meier estimates, hazard ratios and 95% confidence intervals will be reported for each subgroup category if at least 15 events have occurred within the subgroup category. A test of interaction between treatment and each subgroup will be performed in a Cox proportional hazards model with factors for treatment,

subgroup and the interaction between treatment and subgroup for each subgroup where at least 15 events have occurred in each category.

Table 1 **Characteristics and categories for subgroup analysis of the primary composite endpoint**

Characteristic	Categories
Age (years)	< 65, 65-75, >75
Sex	Male, Female
Race	White, Black or African American, Asian, Other
BMI (kg/m ²)	≤ 30, >30
Geographic region	Asia and Australia, Europe and South Africa, North America, Central and South America
ASA use at randomisation	Yes, No
ASA dose at baseline (mg)	≤81, >81
HbA1c at baseline (%)	≤ 7, > 7
eGFR (MDRD) at baseline (mL/min/1.73 m ²)	≤ 60, > 60
Insulin use at baseline	Yes, No
History of Angina	Yes, No
Multivessel Coronary Artery Disease (>1 vessel)	Yes, No
History of PCI	Yes, No
Type of stent	PCI and any DES (including patients with both DES and BMS), PCI and BMS, PCI without stent implantation
History of CABG	Yes, No
History of Coronary Arterial Revascularisation	Yes, No
Statin use at baseline	Yes, No
PPI use at baseline	Yes, No
Current smoker	Yes, No
Duration of diabetes (years)	≤10, >10
History of any diabetes complications at baseline	Yes, No
Number of prior diabetes complications	0, 1, 2, 3-4
History of Peripheral Arterial Occlusive disease	Yes, No
History of Poly-vascular disease	Yes, No
Number of prior vascular beds	1, 2, 3
Time since most recent PCI (years)	<1, 1-3, >3

Characteristic	Categories
Time since most recent CABG (years)	≤ 5 , > 5

BMI = Body Mass Index, BMS = Bare metal stent, CABG = Coronary Artery Bypass, DES = Drug eluting stent, eGFR = estimated Glomerular Filtration Rate, HbA1c = Haemoglobin A1c, MDRD = Modification of Diet in Renal Disease, PCI = Percutaneous Coronary Intervention, PPI = Proton Pump Inhibitor. Baseline is defined as before or at the day of randomisation visit. Poly-vascular disease is defined as history of more than one vascular bed (out of the three possible vascular beds: coronary arterial disease, peripheral arterial occlusive disease, and carotid artery stenosis or cerebral revascularisation.

In addition to subgroup characteristics listed in Table 1, analyses in a specific country subgroup may be done and reported separately to meet requirements for regulatory submissions to local authorities.

4.2.2 Secondary efficacy variables

The secondary efficacy variables will be analysed using the methodology described in Section 4.1. The analyses in section 4.2.1.2 will be repeated for the secondary efficacy variables.

4.2.3 Confirmatory analysis

The analysis of the primary variable described in Section 4.2.1 and the four secondary efficacy variables listed in Section 3.2.2 will comprise the confirmatory analysis. In order to address the issue of multiple testing a hierarchical test sequence will be used. The sequence will start with the primary variable and then follow in the order specified in Section 3.2.2.

The testing at the interim analysis will be at the two-sided 0.1% significance level, while a two-sided 4.96% significance level will be used at the final analysis. In what follows the testing at the final analysis is described, while further detail about the testing at the interim analysis is provided in Section 5.

Only if the treatment effect on the primary efficacy variable is significant at the two-sided 4.96% significance level, will the secondary efficacy variables be tested in a confirmatory sense in the order given in Section 3.2.2. The hypothesis testing will continue at the two-sided 4.96% significance level until the first statistically non-significant treatment difference ($p \geq 0.0496$) is observed. Secondary efficacy variable will be tested in an exploratory manner if there has been at least one non-significant test earlier in the sequence.

4.2.4 Exploratory efficacy variables

Time to event variables will be analysed using the methodology described in Section 4.1.

4.2.5 Health Economics

The variables collected to support health economic evaluation are the EQ-5D questionnaire, administered every 6 months at on-site visits from Visits 2 throughout the study until SCV, and health care resource utilisation data for hospitalisations will be presented descriptively for the FAS per treatment. Further details and other health economic analyses will be specified in

a separate health economic analysis plan and presented in a separate report and are therefore not addressed in this SAP.

4.2.6 Analysis of safety data

All safety analyses will be based on the safety analysis set defined in Section 2.1.2.

Exposure to study drug, reasons and time to discontinuation of study drug, local laboratory data at baseline and vital signs will be summarised per treatment group using descriptive statistics.

4.2.6.1 Bleeding events

Bleeding events will be categorised on the basis of

- Category according to TIMI and PLATO definitions (as defined in the CEC charter), BARC bleeding profiles
- Provocation (ie, spontaneous, procedural and traumatic).

Bleeding events will be summarised by treatment group. The number of transfused blood units will be summarised per treatment group.

The total number of bleeding events, counting multiple events per patient, will be presented.

4.2.6.2 Time to event analysis of bleedings

Time to bleeding event variables will be analysed using the same methodology as for the efficacy variables as described in Section 4.1.

Explorative analysis of time to bleeding for selected subgroups will be performed for the main bleeding categorisations (TIMI major, TIMI major or minor, and PLATO major). Subgroups will be the groups defined for the efficacy analysis in Section 4.2.1.2.

Sensitivity analysis of TIMI major bleeding to address the consistency of the overall effect of ticagrelor on bleeding compared to the 60 mg dose will be performed with a Cox proportional hazards model with time dependent covariates, as described in Section 4.2.1.1 for the primary variable.

Furthermore, a sensitivity analysis of TIMI major bleeding on-treatment in patients randomised to ticagrelor 60 mg or ticagrelor 60 mg placebo and in patients randomised to ticagrelor 90 mg or ticagrelor 90 mg placebo will be performed. These analyses include events that occur up to and including 7 days after last randomised dose of study drug, and event free patients will be censored at the earlier of 7 days after last randomised dose of study drug, last contact, death, SCV or withdrawal of consent.

A landmark analysis of TIMI major bleeding to explore the consistency of treatment effect over treatment dose will be performed. In the analysis, the incidence of TIMI major bleedings

when the patients are treated with ticagrelor 90 mg or ticagrelor 90 mg placebo, and when patients are treated with ticagrelor 60 mg or ticagrelor 60 mg placebo for patients who were event free up to the day of the first 60 mg dose are examined.

4.2.6.3 SAE and non-serious AE of interest

Each AE will be assigned to on/off treatment period as

- Baseline period: The time before randomisation
- On treatment: The time from randomisation until 7 days after last dose study drug
- Off treatment: More than 7 days after last dose of study drug.

AEs will be assigned to the period where they start.

AEs of interest, DAEs as well as SAEs will be evaluated. Summaries, by system organ class and preferred term using MedDRA, will be presented by treatment group using descriptive statistics. All AEs relating to bleeding will be summarised separately. A subset of these summaries will be repeated for patients randomised to ticagrelor 60 mg or ticagrelor 60 mg placebo as a sensitivity analysis.

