To explore effects on quality of life, EQ-5D will be used. It has been extensively used within CV research to assess patient health related quality of life in trials of new treatments, and has showed both high validity and reliability (Brooks 1996).

In PEGASUS, both the 90 mg and 60 mg regimens of ticagrelor were superior to placebo in the prevention of thrombotic CV events (composite endpoint: CV death, MI and stroke) with a consistent treatment effect over the entire study period, yielding a 15% RRR for 90 mg and 16% RRR for 60 mg. Although the efficacy profiles of ticagrelor 90 mg and 60 mg were similar to each other, there is evidence that the lower dose has a better tolerability and safety profile in relation to dyspnoea and risk of bleeding, and leads to fewer discontinuations from

study drug. No patient subgroups were identified as having a different efficacy and safety profile to that of the overall study population.

The critical endpoints selected for the benefit-risk assessment were all-cause mortality, MI, and stroke, which are considered against the risks of fatal bleeding and intracranial haemorrhage, all describing irreversible harm events. For the composite endpoints representing death or irreversible harm, both ticagrelor doses clearly showed a positive benefit-risk balance, with more events of death or irreversible harm prevented than caused. For the ticagrelor 60 mg group, all-cause mortality, CV death, MI and stroke all contributed to the benefit. For the ticagrelor 90 mg group, CV death, MI and stroke all contributed to the benefit, while all-cause mortality was neutral.

In PEGASUS, the efficacy profiles of ticagrelor 90 mg and 60 mg administered with low-dose ASA, were similar to each other. The lower dose had a better tolerability profile with regard to dyspnoea, less risk of bleeding, and lead to fewer discontinuations from study drug. Patients with diabetes did not have a different efficacy and safety profile to that of the overall study population. Hence, in order to use the lowest effective dose and taking the overall benefit-risk into consideration the dose in THEMIS will be ticagrelor 60 mg bd.

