1.2 Study design

The study is event-driven and 19000 randomised patients are estimated to be required in order to collect 1385 adjudicated primary endpoint events. The anticipated maximal duration of treatment with study medication for an individual patient is 58 months. However, the actual duration of the study will be based on accrual of the pre-determined number of adjudicated primary endpoint events, and therefore the study may be shorter or longer than 58 months. The expected minimum follow-up period is 29 months and the expected average follow-up period is 40 months, based on an enrolment period of 28 months. A study closure plan will be developed that accounts for the patient recruitment pattern and the event rate to reach the predetermined number of adjudicated primary endpoint events (1385).

As safety is continuously monitored, the study may be terminated early if either a clear beneficial or harmful effect of the study treatment is detected during the Data Monitoring Committee (DMC) review.

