1.3 Number of subjects

Based on clinical studies and epidemiological information, the event rate for the composite of CV death, MI or stroke has been estimated to be 2.5% annually in a population consisting of patients with T2DM at high risk for CV events without previous medical history of MI or stroke.

The final primary treatment comparison will be made at a significance level of 4.96% adjusted for the planned efficacy interim analysis. Assuming a true hazard ratio (HR) of 0.84 between ticagrelor and placebo, 1385 primary endpoint events will provide a power of 90%.

With an annual event rate of 2.5% in the placebo treatment group, 19000 patients, randomised in a 1:1 ratio, with an average follow-up period of 40 months, are estimated to provide the required number of primary events. The expected minimum follow-up period is 29 months, based on an enrolment period of 28 months.

The expected number of patients who will be lost-to-follow-up is negligible and hence not considered in the determination of samples size.

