4. ANALYSIS METHODS

4.1 General principles

Clinical events reported after database lock will not be included in the primary efficacy and safety analysis.

For time to event variables, treatments will be compared using a Cox proportional hazards model with a factor for treatment group, using the Efron method for ties. Censoring principles are described in Section 4.1.1. The p-values (calculated using the Wald test), HR and 95% confidence intervals for the HR will be reported. Summary tables of these analyses will also include the number of patients with an event and Kaplan-Meier estimates of the event rates per treatment group estimated at a time point determined on the basis of the available follow-up. Kaplan-Meier estimates of the cumulative proportion of patients with events will be estimated and plotted, with the number of patients at risk indicated below the plot at specific time points. If the total number of events in an endpoint or subgroup category is <15, only percentage of patients with events will be presented, but no Kaplan-Meier estimates, HRs, confidence intervals or p-values.

The primary and secondary efficacy variables will be included in a confirmatory testing procedure described in Section 4.2.3. No further multiplicity adjustment will be made to

confidence intervals or p-values. Analyses of efficacy or safety variables that are not part of the confirmatory analyses are considered exploratory and any p-value and confidence interval will be used as a measure of precision only.

In addition to specific analyses and presentations that are detailed in the following sections, results will be summarised using descriptive statistics, including the number of patients, mean, standard deviation, median and range as appropriate. For categorical variables counts and percentage per treatment group will be presented. Summaries of continuous variables will be based on non-missing observations. Percentage for categorical variables will be calculated based the total number of patients in the treatment group, i.e. the denominator includes the number of patients with missing values for the variable.

Demographic characteristics, qualifying risk factors and other specific medical and surgical history will be summarised for the FAS using descriptive statistics.

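### The SAP does not say which period the AE-of-interest and SAE tables cover; on-treatment crude percentages would favour ticagrelor if it is stopped more often than placebo

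*SAP*

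**What the plan says.** SAP 4.2.6.3 assigns each AE, by its start date, to a baseline, on-treatment or off-treatment period. On-treatment runs from randomisation to 7 days after last dose. The planned output is: "Summaries, by system organ class and preferred term using MedDRA, will be presented by treatment group using descriptive statistics". Which of the periods the tables use is not stated. Protocol 12.2.2.2 is equally brief.

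The general rule for percentages is in SAP 4.1: "Percentage for categorical variables will be calculated based the total number of patients in the treatment group". Neither document plans patient-year rates, Kaplan-Meier estimates or hazard ratios for dyspnoea, renal impairment, bradyarrhythmia, gout, pneumonia or SAEs.

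Bleeding is treated differently. SAP 4.2.6.2 analyses it with the Cox and Kaplan-Meier methods used for efficacy, and SAP 4.1.1 censors patients without a bleed at the earliest of several dates, one of which is 7 days after last dose.

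Treatment duration is reported, but separately. SAP 4.2.6 lists "Exposure to study drug, reasons and time to discontinuation of study drug" among the items summarised by arm.

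**The concern.** Protocol 6.4.1.1 says that the long-term effects of ticagrelor on the five AEs of interest will be assessed. Average follow-up is 40 months and anticipated maximum treatment 58 months. An on-treatment window closes when the patient stops drug, so its length is itself affected by treatment. Dividing by patients rather than by time at risk then lowers the percentage in whichever arm is treated for less time.

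Shorter treatment on ticagrelor is plausible from the documents. Protocol 1.4 names bleeding and dyspnoea as the most commonly reported AEs on ticagrelor and reports more TIMI Major bleeding than on placebo in PEGASUS. Protocol 6.4.5.2 requires study drug to be stopped for a clinically significant bleed. In that case an AE with the same hazard in both arms would look somewhat rarer on ticagrelor, and a real excess would look smaller.

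The SAP already has a method that handles unequal time. Its amendment history records that the AE treatment period was redefined to agree with the safety time-to-event analyses, so AEs now share the bleeding window but not the bleeding analysis.

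**Working it through.** **1. Design figures.** The AE section gives no figure of its own, so I first checked the design figures used below.
- SAP 1.3 sets a two-sided alpha of 4.96%, and its power statement (in per cent) reads: "Assuming a true hazard ratio (HR) of 0.84 between ticagrelor and placebo, 1385 primary endpoint events will provide a power of 90".
- Schoenfeld events = 4 × (1.9634 + 1.2816)² / (ln 0.84)² = 1386. Power with 1385 events is 0.900. The plan's figure reproduces.
- SAP 1.3: "With an annual event rate of 2.5% in the placebo treatment group, 19000 patients, randomised in a 1:1 ratio", hence 9500 per arm. SAP 1.2: "The expected minimum follow-up period is 29 months and the expected average follow-up period is 40 months, based on an enrolment period of 28 months".

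**2. Assumptions (not in the documents).** Constant AE hazard h and constant permanent-discontinuation hazard d in each arm.

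For follow-up T:
- crude on-treatment risk = h/(h+d) × (1 − exp(−(h+d)T))
- mean treatment time = (1 − exp(−dT))/d

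**3. Hand check at T = 40 months (3.333 years).** Suppose 20% stop on placebo and 30% on ticagrelor, with h = 0.02 per year in both arms.
- d = −ln(0.80)/3.333 = 0.0669 and −ln(0.70)/3.333 = 0.1070.
- Placebo: 0.02/0.0869 × (1 − exp(−0.2898)) = 5.79%.
- Ticagrelor: 0.02/0.1270 × (1 − exp(−0.4233)) = 5.44%.
- Crude RR = 0.94. Mean treatment time is 2.99 vs 2.80 years, also a ratio of 0.94.
- With 9500 per arm, z = −1.1.

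**4. Range.** Here T is uniform on 29 to 57 months (stated minimum, plus the 28-month enrolment) and h = 0.02 per year. An early-stop fraction of 5%, where used, is given 0.15 years on drug.

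| Discontinuation per year, placebo vs ticagrelor | Mean years on drug | Crude % | Crude RR, true HR 1.00 | Crude RR, true HR 1.20 |
|---|---|---|---|---|
| 8% vs 10% | 3.102 vs 2.996 | 5.99 vs 5.79 | 0.97 | 1.152 |
| 8% vs 12% | 3.102 vs 2.895 | 5.99 vs 5.60 | 0.93 | 1.113 |
| 8% vs 12% + 5% early stops on ticagrelor | 3.102 vs 2.757 | 5.99 vs 5.33 | 0.89 | 1.061 |
| 10% vs 15% + 5% early stops on ticagrelor | 2.996 vs 2.622 | 5.79 vs 5.07 | 0.88 | 1.045 |

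Uniform 29 to 57 months averages 43 months. Uniform 26 to 54 months averages the stated 40 and gives 0.97, 0.94, 0.89 and 0.88; no ratio moves by as much as 0.01. Over both follow-up ranges and AE rates of 1% to 3% per year, a true HR of 1.20 shows as about 1.04 to 1.16.

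**5. Where the bias vanishes.**
- Equal discontinuation (20% vs 20%): crude RR 1.00.
- Hazard confined to month 1: true risk ratio 1.951; crude 1.948 at 20% vs 30% and 1.944 at 20% vs 40%.

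**6. When a false benefit would look significant.** With no true effect at 20% vs 30%, an AE at 1% per year gives z = −0.75, and z reaches −2.4 only at 10% per year. At 20% vs 40%, an AE at 2% per year gives 5.79% vs 5.06% (z = −2.2).

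**The case against.** The strongest objection is that SAP 4.2.6.3 never limits the tables to on-treatment events. Protocol 6.4.3 collects AEs of interest and SAEs to the SCV, and patients who stop drug stay in follow-up. If all events to the SCV are tabulated, the mechanism largely disappears. This stands, and is why the point is conditional and starts with the unstated period.

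Several stronger readings are tempting, but the documents do not support them.
- **That treatment time will be unequal and risks will be understated.** No discontinuation rate by arm is given. Protocol 3.2 says "The lower dose had a better tolerability profile with regard to dyspnoea, less risk of bleeding, and lead to fewer discontinuations from study drug", but this compares 60 mg with 90 mg, not ticagrelor with placebo.
- **That a spurious pneumonia benefit is foreshadowed.** Protocol 1.1.3 reports fewer deaths after pulmonary AEs than on clopidogrel in ACS patients. That says nothing about pneumonia incidence.
- **That DAEs are distorted in the same way.** A DAE itself ends treatment and helps create the exposure gap, so the equal-hazard, shorter-exposure argument does not carry over.
- **That every AE of interest is affected.** Early-onset AEs are not. Protocol 1.1.3 places the excess of ventricular pauses in the first week.

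No test is planned for these AEs, and SAP 4.1 treats non-confirmatory p-values and intervals as measures of precision only. Exposure by arm is also reported. Both soften the point, but a reader cannot recover time to first event for a given AE from an overall exposure table.

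Patient-year rates have their own fault. In the month-1 example at 20% vs 30%, dividing by treatment time turns a nearly correct crude ratio into 1.948 × 2.99/2.80 = 2.08, which overstates harm. Crude n (%) must therefore stay in the tables.

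**Conclusion.** The point holds in conditional form. The SAP leaves the tabulated period open and plans only crude percentages for AEs of interest and SAEs, while bleeding gets a censored analysis under a 7-day rule.

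If the tables are on-treatment and ticagrelor is stopped more often, AEs that accrue over time are biased in ticagrelor's favour by about 3% to 12% in relative terms (crude RR 0.97 to 0.88 at equal hazard). The lower end of that range needs an added 5% of near-immediate stops on ticagrelor alone; without them, 8% vs 10% and 8% vs 12% per year give 0.97 and 0.93.

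All of this rests on assumed discontinuation rates and constant hazards. The effect is modest and would seldom produce a nominally significant false benefit for an uncommon AE. It is still worth correcting, because long-term effects on five named AEs are to be assessed and the method is already in the SAP.

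**What to change.** In SAP 4.2.6.3:
1. State for each table whether it counts on-treatment events or all events to the SCV.
2. Keep n (%) in the tables.
3. For AEs of interest and SAEs, add events per 100 on-treatment patient-years by arm.
4. For the five AEs of interest, apply the Cox and Kaplan-Meier method of SAP 4.1 with the bleeding censoring rule of SAP 4.1.1 (7 days after last dose), and add a parallel analysis of all events to the SCV. The second analysis matters because on-treatment censoring assumes that stopping drug is unrelated to AE risk.

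DAEs can stay as planned.

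The cost is SAP wording, a few table columns and the added outputs for five AEs. AE start dates, the date of last intake and follow-up to the SCV are already collected (Protocol 5.9 and 6.4.3). The downsides are slightly longer tables and the constant-hazard assumption behind patient-year rates; for early-onset AEs these should be read beside the Kaplan-Meier curves.

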5. INTERIM ANALYSES

One efficacy interim analysis will be performed by the DMC. The DMC charter contains more information about the DMC procedures. A copy of the treatment codes will be made available to the statistician on the DMC. The Executive Committee and AstraZeneca will not be made aware of the treatment codes until after clean file and database lock are declared. Similarly, all summary output reviewed at each DMC meeting will be held in confidence by the DMC members until the end of the study when clean file and database lock are declared.

The interim analysis will be performed following the accrual and confirmation by adjudication of 517 primary events. The stopping boundary at the interim analysis is a two-sided p-value <0.001 for both primary endpoint event (CV death, MI, and stroke) and for CV death (the 1st secondary efficacy variable). The interim p-value is small enough for the final analysis to be conducted at a significance level of 4.96%, with the family wise error rate controlled at 5.00%. These boundaries were estimated using a Haybittle-Peto procedure (Haybittle 1971, Peto 1976).

If a recommendation to stop the study is made at the interim, all subsequent testing will be done at the same significance level as for the interim.

